4.3.3.4 Sensitivity/Supplementary analysis

The following sensitivity and supplementary analyses that are planned for the primary efficacy endpoint will also be conducted for the secondary efficacy endpoints:

- Pattern mixture model
- Censoring after intercurrent events
- Per-protocol analysis
- Slope analysis
- Divergence effect analysis

4.3.4 Tertiary Endpoints for Efficacy and Quality of Life

The baseline value and the change from baseline at each post-baseline visit for NPI-10 will be summarized by treatment group. An MMRM model will be used to analyze the change from baseline in NPI-10 using fixed effects of treatment group, time (categorical), treatment group-by-time interaction, baseline NPI-10, baseline NPI-10 by time interaction, baseline MMSE, AD symptomatic medication use at baseline (yes/no), region, and laboratory ApoE \$\pmu 4\$ status (carrier/non-carrier). Same methods as in the primary analysis will be considered for the covariance structure and the degrees of freedom.

For the following tertiary endpoints for patient-reported outcomes and quality of life, subject self-reported EQ-5D index score (SR), informant-rated subject EQ-5D index score (IR-S), and mPDQ-20, the baseline value and the change from baseline at each post-baseline visit will be summarized by treatment group. Additional analyses for these endpoints will be provided in a separate document.

4.3.5 Subgroup Analysis

Subgroup analyses will be performed for the primary endpoint (CDR-SB) and secondary endpoints (MMSE, ADAS-Cog13, ADAS-ADL-MCI). The following pre-defined subgroups will be considered:

- Laboratory ApoE & status (carrier or non-carrier)
- Baseline clinical stage (MCI due to AD or mild AD) per the Investigator's assessment based on the National Institute on Aging-Alzheimer's Association (NIA-AA) criteria
- Use of AD symptomatic medication at baseline (yes or no)

Final V1.0

- Baseline MMSE (MMSE \leq 26 or MMSE \geq 27)
- Region (US, Europe/Canada/Australia, Asia; see Section 4.2.1 for definition of region)
- Age category ($\leq 64, 65-74, \geq 75$)
- Gender (female or male)

A selective set of subgroup analyses will be performed for Amyloid PET data. Details will be defined in Sections 4.4.

4.4 Amyloid PET Analysis

4.4.1 Amyloid PET substudy

Every subject enrolled into the study must have a positive amyloid PET scan by visual read either at screening or obtained within 12 months of screening. Subjects enrolled into the amyloid PET substudy will have the quantitative standard uptake value ratio (SUVR) scores at screening and at each planned post-baseline visit. The amyloid PET substudy will include a subset of approximately 400 subjects in countries other than Japan where PET scans will be performed using ¹⁸F-florbetapir ligand, and a small subset of subjects in Japan where either ¹⁸F-florbetapir ligand or ¹⁸F-flutemetamol ligand will be used. In the placebo-controlled period, amyloid PET assessments are scheduled at screening, Week 26, and Week 78.

4.4.2 Amyloid PET SUVR regions-of-interest and reference regions

Amyloid PET standardized uptake value ratio (SUVR) is a quantitative measure of cerebral amyloid plaque burden. The SUVR will be calculated for the following target brain regionsof-interest (ROIs): composite ROI, frontal cortex, parietal cortex, lateral temporal cortex, sensorimotor cortex, anterior cingulate cortex, posterior cingulate cortex, medial temporal cortex, occipital cortex, striatum, and statistical ROI normalized to reference region activity. Additionally, SUVR ROIs including pons and deep subcortical white matter which are believed to be least affected by amyloid pathology will also be evaluated. The composite ROI will comprise of major cortical regions part of the frontal, parietal, lateral temporal, sensorimotor, anterior, posterior cingulate and occipital cortices to serve as a summary measure of global cerebral amyloid burden. The statistical ROI is a region of interest consisting of the posterior cingulate cortex, precuneus and medial frontal cortex that has been demonstrated to yield optimal group separation between subjects with low and high amyloid burden across different reference regions. A negative change from baseline in composite ROI SUVR indicates a reduction in amyloid burden and a negative treatment difference (aducanumab minus placebo) favors aducanumab. The composite ROI will serve as the ROI of primary focus.

The following reference regions will be employed: cerebellum, cerebellum cropped, cerebellar white matter, cerebellar grey matter, deep subcortical white matter, pons, cerebellum + pons, cerebellar white matter + pons, deep subcortical white matter + cerebellum, deep subcortical white matter + pons and deep subcortical white matter + cerebellum + pons. Cerebellum will serve as the reference region of primary focus.

Final V1.0

The composite ROI SUVR using cerebellum as the reference region will be used as the primary endpoint for amyloid PET analysis.

4.4.3 Amyloid PET analysis population

There are two amyloid PET analysis population: ¹⁸F-florbetapir amyloid PET analysis population and ¹⁸F-flutemetamol amyloid PET analysis population.

The following background characteristics tables will be generated for the ¹⁸F-florbetapir amyloid PET analysis population and will be presented by treatment group: number of subjects enrolled by region and country, demography, baseline disease characteristics, medical history. The content of these tables will be the same as those described in section 4.2 for the ITT population, with the addition of baseline amyloid PET SUVR values summarized for the baseline characteristics of AD.

4.4.4 By visit summary and MMRM model

The baseline and change from baseline amyloid PET SUVR values will be summarized by treatment groups (placebo, low dose and high dose) and by visit for each of the target ROIs using cerebellum as the reference region for each of the amyloid PET analysis populations. In addition, the baseline and change from baseline amyloid composite ROI values will be summarized by treatment groups by visit for each of the reference regions for each of the amyloid PET analysis populations.

For the ¹⁸F-florbetapir amyloid PET analysis population, an MMRM model will be used to analyze change from baseline SUVR for each target ROI with cerebellum as the reference region. Fixed effects of the model will include treatment groups (placebo, low dose and high dose), visit (Week 26 and Week 78), treatment group-by-visit interaction, baseline SUVR (continuous), baseline SUVR by visit interaction, baseline MMSE (continuous), laboratory ApoE & status (carrier and non-carrier), and baseline age (continuous). Visit and treatment group will be treated as categorical variables in the model along with their interactions. An unstructured covariance matrix will be used to model the within-patient variance-covariance errors. If the unstructured covariance structure matrix results in a lack of convergence in any of the parameters, the heterogeneous Toeplitz covariance structure followed by the heterogeneous first-order autoregressive covariance structure will be used for all the parameters. The Kenward-Roger approximation will be used to estimate the denominator degrees of freedom. Adjusted means for each treatment group, pairwise adjusted differences with placebo, 95% confidence intervals for the differences and associated p-values will be presented at week 26 and week 78. The same MMRM model will also be used to analyze the change from baseline SUVR for the composite ROI with each of the reference regions. No multiple comparison adjustment will be used for amyloid PET analysis.

Subgroup analysis will be conducted on the ¹⁸F-florbetapir amyloid PET analysis population using the same MMRM model for composite ROI using cerebellum as reference region for the following stratification factors: laboratory ApoE status (carrier or non-carrier, and this model will not use ApoE status as a covariate), baseline clinical stage (MCI due to AD or mild AD) and baseline composite ROI SUVR value in quartiles.

Visit windows for by visit analysis

Final V1.0

For amyloid PET by visit summaries and MMRM models, the analysis visit should be defined using visit windows (see Table 4 below). The rationale is to use the same analysis visit windows as for the efficacy endpoints for Week 26 and Week 78. If there is more than 1 value in the same analysis visit window (>1 value for the same analysis visit) for a certain parameter for a subject, then the closest record to the target visit day will be used for the by visit analysis. If they are with the same distance from the target visit day, then the record with the later time will be used for the by visit analysis.

Table 4: Visit Windows for amyloid PET data

Analysis visit	Target visit day	Analysis visit window		
Baseline	1	Most recent non-missing pre-dose value		
Week 26	183	[92, 266]		
Week 78 547 [449, the end day of the placebo-controlled period**]				
* The end day of the placebo-controlled period is the last day before the first infusion in LTE for				

subjects who enter in LTE, and is the last day in study for subjects who do not enter LTE.

4.4.5 Correlation between amyloid PET and CDR sum of boxes

Pearson and Spearman correlation

Pearson and Spearman correlations between change from baseline amyloid PET composite ROI using cerebellum as reference region at Week 78 and change from baseline CDR-SB at Week 78 will be conducted by treatment groups (placebo, low dose and high dose, and active total) in the ¹⁸F-florbetapir amyloid PET analysis population. Pearson and Spearman partial correlations adjusting for baseline amyloid PET composite ROI and baseline CDR-SB will also be conducted by treatment groups at Week 78. The estimated correlation coefficients, p-values and the 95% confidence intervals will be provided. Given that reductions in cerebral β-amyloid (Aβ) content may precede clinical effects (e.g., slowing of clinical decline), Pearson and Spearman correlations and partial correlations between change from baseline amyloid PET composite ROI at Week 26 and change from baseline CDR-SB at Week 78 will also be conducted.

Correlation analysis will be done on each individual study as well as in the pooled data of the 221AD301 and 221AD302 studies. The correlation analysis based on the pooled data will be considered as the primary analysis.

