1.3 Tertiary Objectives and Endpoints

1.3.1 Tertiary Objectives

Safety and Tolerability

- To assess the safety and tolerability of monthly doses of aducanumab.
- To assess the immunogenicity of aducanumab.

Biomarker/Efficacy/Quality of Life

Final V1.0

- To assess the effect of aducanumab on cerebral amyloid plaque content as measured by amyloid positron emission tomography (PET) imaging (in a subset of approximately 400 subjects).
- To assess the effect of aducanumab on behavior as measured by the Neuropsychiatric Inventory-10 (NPI-10).
- To assess the effect of aducanumab on subject health status, measured by EuroQol health status measures (EQ-5D [informant-rated and subject self-reported]).
- To assess the effect of aducanumab on subject self-reported cognitive function, measured by the modified Perceived Deficits Questionnaire-20 (mPDQ-20).
- To assess the correlation between primary endpoint and cerebral amyloid plaque content as measured by PET imaging.

Pharmacokinetics

• To collect and characterize the pharmacokinetic (PK) parameters of aducanumab in serum

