4 STATISTICAL ANALYSIS METHODS

4.1 General Considerations

This statistical analysis plan (SAP) only covers the analyses for the primary, secondary and tertiary objectives for the placebo-controlled portion of the study. Hereafter, the placebo-controlled portion of the study will be referred to as "the study" in the rest of this SAP (e.g.,

Final V1.0

completion of the study means completion of the placebo-controlled portion). A separate SAP will be prepared for the analyses of the LTE period and integrated analyses across both portions of the study. The analyses of additional exploratory endpoints will be documented separately.

Summary tables will be presented using descriptive summary statistics. For continuous variables, summary statistics will generally include: number of subjects with data, mean, standard deviation, median, 25% percentile, 75% percentile, minimum and maximum. For categorical variables, this will generally include: number of subjects randomized or dosed, number with data, and the percent of those with data in each category.

There are two types of analysis displays for tables: by treatment group (analysis display A in Appendix 6.1) and by treatment group stratified by ApoE status (analysis display B in Appendix 6.1; here ApoE status refers to the status recorded in IXRS [see Table 1 for correspondence between treatment groups and treatment groups stratified by ApoE status]). The analysis display for each analysis will be defined in each section. All the listings will be presented by treatment group stratified by ApoE status, unless otherwise specified.

Unless otherwise specified, baseline value is defined as the most recent non-missing measurement collected prior to the first dose. Change from baseline will be defined as post-baseline value minus baseline value.

Unless stated otherwise, all statistical tests will be 2-sided with statistical significance level of 0.05.

The statistical software, SAS® will be used for all summaries and analyses.

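### The active-total amyloid PET and CDR-SB correlation in SAP 4.4.5 has no term for dose group or study, so differences in means can produce it without any subject-level link

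*SAP*

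**What the plan says.** Section 1.3.1 lists as a tertiary objective: "To assess the correlation between primary endpoint and cerebral amyloid plaque content as measured by PET imaging". Section 4.4.5 implements it with Pearson and Spearman correlations between change in composite SUVR and change in CDR-SB at Week 78. A second set uses SUVR change at Week 26. All are run "by treatment groups (placebo, low dose and high dose, and active total").

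The adjusted versions are "partial correlations adjusting for baseline amyloid PET composite ROI and baseline CDR-SB". On the two studies: "Correlation analysis will be done on each individual study as well as in the pooled data of the 221AD301 and 221AD302 studies", and "The correlation analysis based on the pooled data will be considered as the primary analysis". On inference: "The estimated correlation coefficients, p-values and the 95% confidence intervals will be provided". Section 4.1 sets the general rule that "all statistical tests will be 2-sided with statistical significance level of 0.05", and Section 4.4.4 adds that "No multiple comparison adjustment will be used for amyloid PET analysis".

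For the active-total column Section 4.4.5 gives no dose-group term, and for the pooled data it gives no study term. It mentions neither stratification nor centring. The PET MMRM in Section 4.4.4, by contrast, does include treatment group.

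**The concern.** A biomarker-outcome correlation is normally read as a statement about subjects: those who lost more amyloid declined less. The active-total column merges two randomised groups given different target doses. If high dose lowers SUVR more than low dose and also gives less CDR-SB decline, the two clouds of points sit apart on both axes, and merging them creates a correlation. Merging two studies whose means differ on both variables does the same.

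Adjusting for baseline does not help, because randomisation balances baseline SUVR and CDR-SB between arms while the differences at issue arise after randomisation.

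What is at stake is interpretation. A significant active-total value could be cited as subject-level evidence when it only restates differences in means that the MMRMs already report.

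**Working it through.** **Inputs from the SAP.** CDR-SB SD 1.92, drop-out 30% and planned difference from placebo 0.5 (Section 3); 1:1:1 allocation (Section 2.1); about 400 PET subjects outside Japan in this study (Section 4.4.1); two-sided 0.05 (Section 4.1).

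**Assumptions not in the SAP.** A similar 400 in 221AD302; 30% without both measures; a high-low separation on SUVR change, dx, of 1 to 2 within-arm SDs; a high-low CDR-SB difference, D, of 0, 0.25 or 0.5.

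**Step 1: check the inputs.** The SAP gives no figure for the correlation analysis. Its power statement reproduces: 450 × 0.7 = 315 per group; 0.5 / (1.92 × √(2/315)) = 3.27; Φ(3.27 − 1.96) = 0.905, against the stated approximately 90%.

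**Step 2: active subjects in the pooled data.** 2 studies × 400 × 2/3 × 0.7 = 373.

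**Step 3: correlation created by merging arms.** Let the correlation be zero inside each of two equal arms, and let dy = D/1.92. Merging adds 0.25·dx·dy to the covariance, and 0.25·dx² and 0.25·dy² to the two unit variances:

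r = 0.25·dx·dy / √[(1 + 0.25·dx²)(1 + 0.25·dy²)]

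For D = 0.5, dy = 0.260. With dx = 1, r = 0.0651 / √(1.25 × 1.017) = 0.058. With dx = 2, r = 0.130 / √(2 × 1.017) = 0.091.

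**Step 4: chance of p < 0.05.** On the Fisher z scale the shift is atanh(r) × √(373 − 3). For r = 0.058 this is about 1.11, so the upper tail is Φ(1.11 − 1.96) = 0.20. For r = 0.091 it is about 1.76, giving Φ(1.76 − 1.96) = 0.42. The lower tail is negligible in both.

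| High-low difference on CDR-SB | dx = 1: r, rejection | dx = 2: r, rejection |
|---|---|---|
| 0 | 0, 5% | 0, 5% |
| 0.25 | 0.029, 9% | 0.046, 14% |
| 0.5 | 0.058, 20% | 0.091, 42% |

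At D = 0.5, a single study (187 active subjects) gives 12% and 24%; pooled data with nothing missing (533) give 27% and 56%.

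**Step 5: does baseline adjustment help?** Simulation with zero within-arm correlation (2,000 runs, 372 active subjects over two studies) says no. At D = 0.5 the baseline-adjusted Pearson and Spearman partial correlations reject in 22-23% (dx = 1) and 49-50% (dx = 2).

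**Step 6: study shifts alone.** With no dose difference, and the studies differing by an assumed 0.5 SD on SUVR change and 0.5 points on CDR-SB, active total rejects in about 10% (9-11% over the four versions). The pooled high-dose column on its own rejects in 7%.

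**Step 7: after the change.** With dose group, study and their interaction partialled out, rejection is 4.8-6.0% in every scenario. That is nominal within simulation error: √(0.05 × 0.95 / 2000) is about 0.5 percentage points.

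**The case against.** Much of the case on the other side stands.

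- The same sentence of Section 4.4.5 plans low-dose and high-dose correlations separately, and the section also plans each study separately. Those per-dose, per-study correlations are free of this artefact, and a reader can compare them with active total.
- The inflation needs a difference in means on both variables. Section 3's blinded sample size re-estimation assumed the same effect in both doses, and under that assumption the dose part is zero. A high-low difference of 0.5 is as large as the whole planned effect versus placebo.
- The spurious coefficient is weak, and it will be printed with its interval.
- The correlation across all treated subjects is a legitimate descriptive quantity. Partialling out dose discards the randomised part of the amyloid variation.
- Section 3 describes the two studies as identically designed; the study shifts used above are assumed.

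Two stronger readings are tempting. A reader might infer that active total is the primary correlation. Section 4.4.5 ranks pooled data above single-study data but does not rank active total above the dose groups. A reader might also infer that the test contradicts a stated null hypothesis. None is stated: the objective speaks only of correlation.

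These points limit the concern but do not remove it. P-values are planned for active total, nothing labels it descriptive, and the pooled single-dose columns also lack a study term.

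**Conclusion.** The point holds as a minor one. As planned, the active-total correlation mixes subject-level association with differences between dose-group means and, in the pooled version, between study means. The baseline-only partial correlations do not separate them.

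Under the stated assumptions a nominal 5% test rejects in about 9-14% of trials at a CDR-SB difference of 0.25 between doses and about 20-42% at 0.5. It is unaffected when the doses have equal CDR-SB effects. The rates depend on the assumed SUVR separation and on the assumed PET subset size in 221AD302, neither of which the SAP gives. The p-value is distorted more than the apparent strength.

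A reader might infer that a confirmatory conclusion is at risk. It is not: the analysis is tertiary, has no multiplicity control and lies outside the sequential testing in Section 4.3.1.

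**What to change.** In Section 4.4.5:

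- For active total, add randomised treatment group to the variables partialled out.
- For every pooled 221AD301 and 221AD302 correlation, add study; for active total, also add the study-by-treatment-group interaction. Alternatively, combine the within-arm, within-study correlations by Fisher z.
- Use this version for any subject-level interpretation, and label the unadjusted active-total value as descriptive.

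The cost is a few extra terms in a partial correlation that is already planned, with no new data. The downside is that the adjusted value no longer reflects the randomised, dose-related part of the amyloid change, which is a reason to keep the unadjusted value alongside it.

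The change has a limit. The near-nominal rates in Step 7 assume homogeneous arms. The low-dose arm mixes dose levels by ApoE status (Section 2.1, Table 1), and the high-dose arm includes some carriers from protocol versions 1-3 who had no opportunity to move to the later target dose (Section 4.3.1). Adjusting for arm does not remove differences in means between those subgroups, and the text should say so.

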4.5 Safety Analysis

4.5.1 General Considerations

Analysis population

Safety population will be used for safety analyses of AEs, clinical laboratory data, Columbia Suicide Severity Rating Scale (C-SSRS) data, ECG data and vital sign data (all the safety data except for ARIA data). Safety MRI population will be used for analyses of ARIA data.

Final V1.0

Safety treatment groups

Different from the randomization treatment groups, if a subject who was randomized to placebo group accidentally received one or more doses of the active treatment during the study, he/she will be classified as either low or high dose group for all the safety analyses, depending on the ApoE status and the maximal dose level of the active treatment received (Table 5). A listing of such subjects will be provided, as described in section 4.2.5. Safety treatment groups will be the same as the randomization treatment groups for other subjects (subjects randomized to active treatment groups, and subjects randomized to placebo without any accidental active dose). Safety treatment groups will be used for all the safety analyses unless otherwise specified.

Table 5: Safety treatment groups for placebo subjects with accidental active treatment

Randomization treatment group	Randomization ApoE status	Safety treatment group classification based on the maximum dose level of the accidental active treatment		
		>0 to 3 mg/kg	>3 to 6 mg/kg	>6 mg/kg
Placebo	ΑροΕ ε4 (+)	Low dose	High dose	High dose
	ΑροΕ ε4 (-)	Low dose	Low dose	High dose

Safety analysis displays

AEs, clinical laboratory data, C-SSRS data, ECG data and vital sign data (all the safety data except for ARIA data) will be summarized by treatment group (placebo, low dose, high dose and BIIB037 total; analysis display A in Appendix 6.1), unless otherwise specified. All the ARIA related tables will be presented by treatment group stratified by ApoE status (3 columns under each treatment group: ApoE ϵ 4+, ApoE ϵ 4- and total; analysis display B in Appendix 6.1), unless otherwise specified. A subset of AE tables will also be presented by treatment group stratified by ApoE status in addition to by treatment group. All the listings will be presented by treatment group stratified by ApoE status.

Incidence, incidence proportion and incidence rate

Incidence and incidence proportion will be provided in incidence tables. Incidence is
defined as the number of subjects who experienced an event. Incidence proportion is
defined as the number of subjects who experienced an event divided by total number of
subjects in the analysis population, i.e., percentage. Each subject will be counted only
once within each category.

Final V1.0

- Incidence and incidence rate will be provided in incidence rate tables. Two different kinds of incidence rate tables will be provided as appropriate for different analyses. Definitions are provided below.
 - (1) Follow-up adjusted incidence rate defined as the number of subjects who experienced an event divided by the total of entire follow-up time among the subjects in the analysis population. The entire follow-up time for a subject is defined as the time from the first dose until the last day on study. Each subject will be counted only once within each category.
 - (2) Exposure-adjusted incidence rate (EAIR) defined as the number of subjects who experience an event divided by the total exposure adjusted follow-up time among the subjects in the analysis population. The exposure adjusted follow-up time is defined as the time from the first dose until the initial occurrence of the event for those who experienced an event, or from the first dose until the end of follow-up (the last day on study) for those who did not. Each subject will be counted only once within each category.

